8. EFFICACY ENDPOINT EVALUATION

8.1. Overview of Efficacy Analysis Methods

8.1.1. Multicenter Studies

Subjects will be enrolled at approximately 50 sites; site identifiers will be included on by-subject listings.

8.1.2. Timing of Analyses

An interim analysis requiring a data freeze in late 2022 will be performed for a New Drug Application (NDA) submission as described in Section 11.

All final, planned analyses will be performed after the last subject has completed all study assessments, all relevant study data have been processed and integrated into the analysis database, and the database has been locked.

Any post hoc, exploratory analyses completed to support planned study analysis, which were not identified in this SAP, will be documented and reported in appendices to the CSR. Any results from these unplanned analyses (post hoc) will also be clearly identified in the text of the CSR.

8.2. Efficacy Endpoint

The efficacy endpoint is the relative change in SALT score over time from baseline. Both the change from the “pre-zero” baseline and the change from the CP543.5002 study baseline will be assessed (see Section 6.2).

8.2.1. Computation of the Efficacy Endpoint

The SALT assessment is a measure of hair loss that quantifies the amount of scalp surface without hair in a pre-specified quadrant of the scalp (right side, top, left side, back), that is further summed after applying a quadrant-specific multiplier indicative of scalp surface area contribution, to provide an overall score of total hair loss. The total score is calculated as [(left quadrant raw score \times 0.18) + (right quadrant raw score \times 0.18) + (top quadrant raw score \times 0.40) + (back quadrant raw score \times 0.24)]. An example of the SALT assessment can be found in Appendix 16.1 of the study protocol.

Absolute change in SALT score is derived as the follow-up SALT score minus the baseline SALT score. Relative change in SALT score is derived as percent change of the follow-up SALT score, where baseline SALT score is the denominator (i.e. absolute change divided by the baseline score, multiplied by 100). Absolute change and relative change from baseline will be computed for both the “pre-zero” baseline and the CP543.5002 study baseline.

Absolute change in SALT score should be rounded to the nearest whole number following its derivation. Relative change in SALT score should be rounded to one decimal place following its derivation.

No imputation will be conducted for missing SALT scores.

8.2.2. Primary Analysis of the Efficacy Endpoint

All efficacy summaries will be descriptive with no statistical hypothesis testing and based on the Efficacy Population.

The observed, absolute change, and relative change from baseline in SALT score will be reported by treatment group and overall, as specified in Section 4. Change from baseline will be presented separately for the “pre-zero” baseline and the CP543.5002 study baseline. The results may also be displayed graphically. By-subject listings for SALT will also be presented.

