Pregnancy testing will be performed every 4-weeks throughout study enrollment. As in-clinic visits are performed bi-monthly following Visit 4 (Week 12), subjects will perform in-home urine pregnancy tests at Week 16, Week 24, Week 32, Week 40 AND Week 48 and 4-weeks post the final study visit. The test date and result will be documented.

In-home pregnancy testing window is  $\pm$  3 days

Collected pre-dose, when possible.

Includes fasted hematology, serum chemistry, SARS-CoV-2 testing, and lipids performed by the central lab.

At the Week 52 visit, patients will be assessed via SALT for treatment success (Responder) defined as having an absolute SALT score of  $\leq 20$  at Week 52. These responders will be eligible to continue in the OLE extension for up to a maximum of one additional year.

Study drug dispensation will occur at Visit 9 (Week 52) for RESPONDERS ONLY (defined as having a SALT score  $\leq 20$ ).

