- Data from each subject will be separated by a blank line. Within a data listing, if a descriptive item appears line after line, only the first occurrence will be displayed (e.g., in Listing of Vital Signs, subject number, date and visit will only be displayed on first row when presenting all parameters collected at same visit). Repetition of actual results or outcomes (e.g., AEs, lab results, vital sign values) will not be collapsed.
- Data listings will be sorted by CTP-543 dose, subject, and date and/or time of assessment, as applicable, unless otherwise specified.
- Whenever change from baseline or change to baseline is calculated, baseline will be defined and presented in two different ways, with a “pre-zero baseline” and a “CP543.5002 study baseline” as described in Section 6.2. Assessments for physical exams, clinical laboratory tests, 12-lead electrocardiograms (ECG), and SALT will be carried over from the preceding clinical trial database into this study database and be used as the subject’s baseline assessment.

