- Total CTP-543

Subjects will further be categorized into “analysis cohorts” based on their prior treatment in the qualifying study (CTP-543 8 mg BID, CTP-543 12 mg BID, or Placebo). Unless otherwise specified in this SAP, efficacy tables will be presented separately by analysis cohort and overall, with treatment groups as columns. If <5 subjects fall under a treatment group for a given analysis cohort, that column will be dropped. All subjects will still be included in the overall column.

Summary tables for exposure, and AEs will include the following treatment columns:

- CTP-543 8 mg BID
- CTP-543 12 mg BID
- Total CTP-543

For analyses of exposure, a subject with a qualifying dose change will be treated as if the subject changed dose from one study to another and will be included under more than one treatment column. For analyses of AEs, AEs will be considered treatment-emergent with respect to the most recent dose taken prior to the start of the adverse event. Subjects may be included in more than one treatment column due to dose changes.

Mock tables and data listings will be provided as attachments to this analysis plan. Minor changes to the mocks after formal SAP approval will not necessitate re-approval unless changes to the text of the SAP are required.

All statistical deliverables will be produced, validated, and reviewed for accuracy/consistency in accordance with [REDACTED] standard operating procedures and the processes described in the statistical validation plan.

SAS® (SAS Institute, Cary, North Carolina) statistical software, version 9.4 or later, will be used for all analyses. Adverse Events and Medical History will be coded in Medical Dictionary for Regulatory Activities (MedDRA) Version 23.1. Concomitant medications will be coded in World Health Organization (WHO) Drug Global Version 2020-SEP and Anatomical-Therapeutic-Chemical (ATC) classification and preferred term.

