8.2.3.1. Analysis of the Efficacy Endpoint Post-Dose Reduction

[REDACTED]

Subjects with loss of response will be defined as having an absolute SALT score > 50 ; subjects with no loss of response will be defined as having an absolute SALT score ≤ 50 . Responders at pre-dose reduction baseline will be defined as having an absolute SALT score ≤ 20 at pre-dose reduction baseline; non-responders will be defined as having an absolute SALT score > 20 . A line graph of the absolute change from pre-dose reduction baseline SALT score vs. visits since dose reduction will also be produced for subjects who had a dose reduction from CTP-543 12 mg to 8 mg on or after 28 Apr 2023 due to the urgent safety measures.

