9.2. Extent of Exposure

Study drug exposure will be summarized for the CTP-543 8 mg BID and CTP-543 12 mg BID treatment groups and overall. Duration of exposure in weeks will be calculated as (date of last dose of study drug minus the date of first dose of study drug + 1 day)/7. Study drug exposure will be summarized categorically by duration of treatment in weeks ($\geq 4, \geq 8, \geq 12, \geq 16, \geq 20, \geq 24, \geq 28, \geq 36, \geq 44, \geq 52, \geq 60, \geq 68, \geq 76, \geq 84, \geq 92, \geq 100$, and ≥ 108) and will include a summary of subjects receiving ≥ 1 dose. Dose interruptions, missed doses, and partial doses will be ignored. Subjects who are lost to follow-up and were on treatment as of their last visit will be counted as receiving their last dose on the date of the last visit completed. Duration of study drug exposure in weeks as a continuous variable will also be summarized.

All summaries of exposure will be limited to exposure in CP543.5002.

Duration of cumulative study drug exposure in weeks for subjects who entered the OLE will be calculated as (OLE treatment end date – OLE treatment start date – the number of days of missed dose + 1)/7. Duration of cumulative study drug exposure will be summarized and calculated in the same manner as study drug exposure, except that any period of dose interruptions or missed doses will be subtracted. If the reason not dosed is “dose interruption”, it will be counted as a missed dose regardless of the actual number of tablets taken. If the reason not dosed is “missed dose” or “partial dose” and no tablets were taken, it will be treated as a missed dose; if the reason not dosed is “missed dose” but 1 tablet was taken, it will be treated as a partial dose.

Duration of exposure up to a qualifying dose change in CP543.5002 will be summarized as a categorical measure based on treatment sequence between the qualifying study and initial dosing in CP543.5002, as follows: Placebo to 8 mg BID, Placebo to 12 mg BID, 8 mg BID to 8 mg BID, and 12 mg BID to 12 mg BID. Duration of exposure up to a qualifying dose change for subjects previously on placebo will be separately tabulated from that of subjects previously on active drug in the qualifying study. For purposes of these tabulations, if a subject experiences a qualifying dose change, duration of exposure will be counted up to the qualifying dose change. Dose interruptions, missed doses, and partial doses will be ignored.

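### Mean SALT and mean change are planned as one series to Week 108, although only patients with SALT ≤20 continue after Week 52, so comparisons across Week 52 mix treatment course with removal of non-responders

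*SAP*

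**What the plan says.** **Who continues.** Protocol 8.4.1 and SAP 3 have patients with SALT above 20 at Week 52 complete the study at that visit. Protocol Table 1, footnote 10, adds: "Study drug dispensation will occur at Visit 9 (Week 52) for RESPONDERS ONLY".

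**What is summarised.** SAP 8.2 states: "The efficacy endpoint is the relative change in SALT score over time from baseline". Under SAP 8.2.2, "The observed, absolute change, and relative change from baseline in SALT score will be reported by treatment group and overall". SAP 5 defines a single Efficacy Population for all visits (at least one dose and one post-baseline SALT), and SAP 8.2.1 rules out imputation of missing SALT.

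**Over which visits.** SAP 8.2.2 does not itself say that the summary is by visit. That follows from the endpoint being defined over time, from Protocol 11.1.2 (by visit, as appropriate) and from SAP 4.2, which places scheduled data at nominal visits and lists efficacy windows to Week 108.

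**Which anchors and columns.** SAP 4: "Whenever change from baseline or change to baseline is calculated, baseline will be defined and presented in two different ways". The two are the pre-zero baseline and the CP543.5002 baseline. One further anchor is visible, in SAP 8.2.3.1: "Responders at pre-dose reduction baseline will be defined as having an absolute SALT score" of 20 or less. That anchor is the dose reduction, not Week 52. By SAP 4.1, "efficacy tables will be presented separately by analysis cohort and overall, with treatment groups as columns"; no column is defined by Week 52 response, and SAP 8.4 plans no subgroups. In the visible text, Week 52 responder status only sets a window bound (SAP 4.2, Table 2, footnote 1).

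**The concern.** After Week 52 the averaged patients have been selected on the variable being averaged. A drop in mean SALT between Week 52 and Week 60 would look like further regrowth, even if no patient had changed. A modest real loss of response in the continuing patients could be hidden inside that drop.

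This matters because the Protocol synopsis names maintenance of hair growth as an evaluation criterion, and relative change in SALT is the only efficacy endpoint in the SAP (8.2, 8.3). The study is descriptive, so its efficacy message rests on how these summaries read.

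**Working it through.** The plan states no expected SALT mean, so there is no figure of its own to reproduce. The clinical stopping rule is taken as given.

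**1. Observed mean.** Let p be the share with SALT ≤20 at Week 52, mR their mean and mN the mean of the others. Suppose all responders continue and nobody changes.

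- Week 52 mean = p·mR + (1−p)·mN
- Week 60 mean = mR
- Fall = (1−p)(mN−mR)

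By definition mR ≤20 and mN >20, so the fall is positive whenever p <1. The sizes below rest on assumed inputs.

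| p | mR | mN | Week 52 mean | Week 60 mean | Fall |
|---|---|---|---|---|---|
| 50% | 8 | 60 | 34 | 8 | 0.50 × 52 = 26 |
| 70% | 15 | 40 | 22.5 | 15 | 0.30 × 25 = 7.5 |
| 29.6% | 5 | 80 | 57.8 | 5 | 0.704 × 75 = 52.8 |

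The lowest p is the Week 24 rate on 8 mg BID in CP543.3001 (Protocol 4.2), used only for orientation.

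**2. Masking.** A simulation of 400,000 patients (p from 0.3 to 0.6, visit noise SD 5) gave these results:

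- With no true change, the planned mean goes from 29.0–44.5 at Week 52 to 8.2–8.7 at Week 60.
- With every continuing patient 10 points worse, it still falls, to 18.2–18.7.
- Followed from their own Week 52 score, with no true change, the same continuers move only from 7.7–8.0 to 8.2–8.7. That is +0.5 to +0.7 points, which is regression to the mean.

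**3. Mean change.** With responder and non-responder mean changes cR and cN, the step at Week 60 is (1−p)(cR−cN).

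- *Pre-zero baseline.* Assume responders go from 80 to 8 (−90.0%), non-responders from 85 to 60 (−29.4%), and p = 50%. The mean goes from −59.7% to −90.0%.
- *CP543.5002 baseline.* Patients already ≤20 at entry have little left to gain. Let e be their share among Week 52 responders, taken as the Week 24 rate divided by p (this assumes that they stay ≤20 and that roll-over patients resemble CP543.3001). Assume that they stay at 8, later responders go from 70 to 8 (−88.6%) and non-responders from 75 to 60 (−20%). Then cR = (1−e)(−88.6%). At p = 50%:

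| Week 24 rate ≤20 | e | Week 52 | Week 60 | Step (points) |
|---|---|---|---|---|
| 0.8% (placebo) | 0.016 | −53.6% | −87.2% | 33.6 apparent gain |
| 29.6% (8 mg BID) | 0.592 | −28.1% | −36.1% | 8.1 apparent gain |
| 41.5% (12 mg BID) | 0.83 | −17.5% | −15.1% | 2.5 apparent worsening |

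The direction reverses only when e exceeds 1 − 20/88.6 = 0.774. For a 41.5% entry rate this needs p below 0.415/0.774, about 54%. The reversal is possible, but it is not an estimate.

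**4. What is not distorted.** SAP 4 sets header N as the default denominator for percentages. Patients above 20 are not in the numerator at Week 52, so their exit does not move the percentage ≤20. SAP 8.2.3 also reports the number ≤20 by visit. After Week 52, everyone counted comes from the Week 52 responders, barring deviations or a missing Week 52 score. Take 100 patients with 50 responders. Assume 5% do not enter, 10% of entrants are unassessed at a later visit and 85% of those assessed are still ≤20. That gives 50 × 0.95 = 47.5 entrants, 42.75 assessed and 36.3 still ≤20.

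| Denominator | Result | From the planned tables? |
|---|---|---|
| Week 52 responders | 36.3/50 = 72.7% | Yes, two rows of one table |
| Patients assessed | 36.3/42.75 = 85% | Yes, shift-table totals |
| Extension entrants | 36.3/47.5 = 76.5% | No, entrant count needed |

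**5. Entrant count.** SAP 6.1 counts completers without separating Week 52 from Week 108. SAP 9.2 helps only in part: "Study drug exposure will be summarized categorically by duration of treatment in weeks". At least 52 weeks means a last dose on day 364 or later. The Week 52 visit window is days 362–368 (365 ± 3), so some non-responders fall in that category with the entrants. The ≥60-week category (day 420 or later) omits entrants who stop sooner.

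**The case against.** The strongest reply is that a careful reader already has what is needed. The exit rule is stated repeatedly in both documents, n accompanies each mean, SALT listings are planned, and graphs are optional. Much of this stands: the n shows that patients left, and the documents themselves say why. It does not repair the summary, because a mean that changes population between adjacent visits cannot be corrected by eye. Deriving a Week 52 analysis later would make it post hoc under SAP 8.1.2, reported in appendices to the CSR.

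Some stronger inferences are tempting and are not supported:

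- *That the whole of Weeks 60–108 is distorted.* Every patient observed there is a continuer, so the exit rule adds no further step. Ordinary dropout remains.
- *That maintenance cannot be obtained.* The planned counts ≤20 give it over all Week 52 responders.
- *That prior-treatment cohorts will show opposite steps side by side.* Cohorts are presented separately, and the reversal depends on assumed inputs.
- *That the SAP certainly contains no Week 52 analysis.* Part of 8.2.3.1 is redacted, and the shells are not available here: "Mock tables and data listings will be provided as attachments to this analysis plan". Neither can be judged.

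No hypothesis is tested, so no error rate is affected.

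**Conclusion.** The point holds for comparisons across Week 52 of mean SALT and of mean change from either baseline. For the observed mean, the direction of the step follows from the responder definition if all responders continue and nobody changes. To cancel it, continuers would have to worsen on average by (1−p)(mN−mR) within eight weeks. Its size cannot be fixed from the documents: 26 points in the central example, 7.5 to 52.8 over the assumed ranges. By-visit reporting to Week 108 is the natural reading of the plan rather than an explicit sentence in SAP 8.2.2.

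The visible text lacks three things: a labelled maintenance display, a change from Week 52, and an exact extension-entrant denominator. This should be fixed because it affects how the only efficacy endpoint is read. It does not invalidate the percentage ≤20 or the responders-only series from Week 60 onwards.

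**What to change.** - **SAP 8.2.2:** end the full-population mean and change summaries, and any curve, at Week 52. Alternatively, show Weeks 60–108 in a separate, unjoined panel labelled *Week 52 responders who continued*.
- **SAP 8.2.3:** add an extension set, defined as patients dispensed drug at Week 52. For Weeks 52–108 report absolute change from each patient's own Week 52 SALT (relative change is undefined when that score is 0). Also report the percentage still ≤20 with entrants as denominator, and the number assessed at each visit. Keep the header-N percentage.
- **SAP 6.1 (optional):** split completion into completed at Week 52 as non-responder, entered the extension, and completed Week 108.

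The cost is SAP wording and one extra table set. No new data are needed: Week 52 status is already derived (SAP 4.2) and dispensing is recorded (Protocol 8.3.5). The new table needs a note that change from Week 52 in patients selected at SALT ≤20 carries a small regression to the mean, about +0.5 to +0.7 points in the simulation above.

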8.2.3. Supportive Analyses of the Efficacy Endpoint

The number and percentage of subjects with an absolute SALT score ≤ 20 will be reported by study visit and treatment group.

A shift table comparing treatment response (responder, non-responder) at baseline to treatment response (responder, non-responder) post-baseline will be produced by visit and treatment group, separately for the “pre-zero” baseline and the CP543.5002 study baseline. Responders will be defined as having an absolute SALT score ≤ 20 ; non-responders will be defined as having an absolute SALT score > 20 .

8.2.3.1. Analysis of the Efficacy Endpoint Post-Dose Reduction

[REDACTED]

Subjects with loss of response will be defined as having an absolute SALT score > 50 ; subjects with no loss of response will be defined as having an absolute SALT score ≤ 50 . Responders at pre-dose reduction baseline will be defined as having an absolute SALT score ≤ 20 at pre-dose reduction baseline; non-responders will be defined as having an absolute SALT score > 20 . A line graph of the absolute change from pre-dose reduction baseline SALT score vs. visits since dose reduction will also be produced for subjects who had a dose reduction from CTP-543 12 mg to 8 mg on or after 28 Apr 2023 due to the urgent safety measures.

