## 1. SYNOPSIS

|   |                                |
|---|--------------------------------|
| Name of Sponsor/Company:
Sun Pharmaceutical Industries, Inc.  |                                |
| Name of Investigational Product:
CTP-543  |                                |
| Name of Active Ingredient:
deuruxolitinib   |                                |
| Title of Study:
A Multicenter, Open-label, Extension Study to Assess the Long-Term Safety and Efficacy of CTP-543 in Adult Patients with Moderate to Severe Alopecia Areata   |                                |
| Study Number: CP543.5002   |                                |
| Study center(s): Multicenter; European Union   |                                |
| Studied period (years):
Estimated date first patient enrolled: September 2021
Estimated date last patient completed: July 2024   | Phase of development: 3 |
| Objectives:
The overall objectives of the study are to evaluate long-term safety of CTP-543 and to assess long-term effects of CTP-543 on treating hair loss in adult patients with moderate to severe alopecia areata.   |                                |
| Methodology:
Patients with alopecia areata who previously participated in a qualifying Phase 3 clinical trial (study CP543.3001 or study CP543.3002) with CTP-543 and who complete the 24-week Treatment Period on Study Medication (active or placebo), have the opportunity to enroll in this open-label extension (OLE) study in which they will receive daily treatment with CTP-543. At the Week 52 visit, patients will be assessed for treatment success (Responders) defined as patients having an absolute SALT score of $\leq 20$ at Week 52. These Responders will be eligible to continue in the OLE extension for up to a maximum of one additional year. Non-responders will complete the study at Week 52.
Safety will be evaluated by clinical laboratory measurements, AEs and physical exams. SARS-CoV-2 testing will be performed at all visits. SALT assessments will be performed periodically for efficacy, as described in the Schedule of Events Tables (Table 1 and Table 2). |                                |

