CTP-543 has been studied in patients with moderate to severe alopecia areata and at least 2 different doses have demonstrated significant hair regrowth over a 24-week treatment period. A Phase 2 dose-ranging clinical trial assessing the efficacy and safety of CTP-543 in moderate to severe AA patients was completed. The overall objectives of the study were to assess the safety and efficacy of a 24-week regimen of administration of 4, 8, or 12 mg BID CTP-543 compared to matching placebo in adult patients with moderate to severe alopecia areata. The primary efficacy endpoint was the proportion of responders, defined as patients achieving at least a 50% relative reduction in SALT score, from Baseline at Week 24. The primary efficacy endpoint was met in both the 8 mg BID group and the 12 mg BID group. The difference between the 4 mg BID group and the placebo group was not statistically significant. The 8 mg BID and 12 mg BID doses also produced significant results vs placebo when other analyses of SALT data were conducted as well as analyses of patient and clinician reported global impression.

In the pivotal phase 3, randomized, double-blind, placebo-controlled study CP543.3001 (THRIVE-AA1) evaluating the efficacy and safety of CTP-543 in adult subjects with moderate to severe AA, both CTP-543 8 mg BID and CTP-543 12 mg BID for 24 weeks resulted in a statistically significant proportion of subjects (29.6% and 41.5%, respectively; versus 0.8% on placebo) who achieved an absolute SALT score  $\leq 20$  at Week 24, a measure that is considered to be clinically meaningful to patients and physicians (Wyrwich et al., 2020). CTP-543 was generally well tolerated at both doses, with the safety profile consistent with that of other drugs of the same class.

Similarly, in the second pivotal phase 3, randomized, double-blind, placebo-controlled study CP543.3002 (THRIVE-AA2) evaluating the efficacy and safety of CTP-543 in adult subjects with moderate to severe AA, both CTP-543 8 mg BID and CTP-543 12 mg BID for 24 weeks resulted in a statistically significant proportion of subjects (33.0% and 38.3%, respectively; versus 0.8% on placebo) who achieved an absolute SALT score  $\leq 20$  at Week 24.

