4.1. Treatment Group Presentation by Analysis

For analyses of disposition, demographics, baseline characteristics, concomitant medications, and medical history, subjects will be analyzed under their first actual treatment received (8 mg BID or 12 mg BID) in CP543.5002. The following treatment columns will be used:

- CTP-543 8 mg BID
- CTP-543 12 mg BID
- Total CTP-543

Summary tables for the laboratory evaluations, vital signs, and ECGs will include the following treatment columns referring to the starting dose in CP543.5002 and modified dose, if applicable (CP543.5002 initial treatment to CP543.5002 modified treatment):

- CTP-543 8 mg BID
- CTP-543 12 mg BID
- CTP-543 8 mg BID to CTP-543 12 mg BID
- CTP-543 12 mg BID to CTP-543 8 mg BID
- Total CTP-543

For analyses of laboratory evaluations, vital signs, and ECGs, the treatment groups CTP-543 8 mg BID and CTP-543 12 mg BID refer to subjects who initially received CTP-543 8 mg BID or CTP-543 12 mg BID, respectively, during CP543.5002 and received no qualifying dose changes. For clarity, for purposes of identifying treatment groups for these analyses, the initial dose will be the first dose that was dispensed for at least 2 visits; if no dose meets that criteria, then the initial dose is the first dose actually received in CP543.5002. A qualifying dose change is any dose change from the initial dose that spans more than one planned visit in CP543.5002 (i.e., the altered dose was dispensed at two or more consecutive visits). The treatment group CTP-543 8 mg BID to CTP-543 12 mg BID refers to subjects who received a qualifying dose change from 8 mg BID to 12 mg BID during CP543.5002. In the event of more than one qualifying dose change, only the first qualifying dose change will be considered. The treatment group CTP-543 12 mg BID to CTP-543 8 mg BID is defined similarly for qualifying dose changes from 12 mg BID to 8 mg BID.

If there are no subjects with dose adjustments meeting the criteria defined above, the CTP-543 8 mg BID to CTP-543 12 mg BID and CTP-543 12 mg BID to CTP-543 8 mg BID columns may be excluded from summaries which utilize the Safety population.

For analyses of efficacy, subjects will be classified in the same treatment groups as above for laboratory evaluations, vital signs and ECGs:

- CTP-543 8 mg BID

Sun Pharmaceutical Industries, Inc.
Statistical Analysis Plan – CP543.5002

- CTP-543 12 mg BID
- CTP-543 8 mg BID to CTP-543 12 mg BID
- CTP-543 12 mg BID to CTP-543 8 mg BID

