6.2. Demographic and Other Baseline Characteristics

Demographic characteristics (i.e. sex, ethnic origin, race, and age) will be collected at the Day 1 visit, which will occur on the same day as their last visit in the preceding clinical trial, and detailed on the eCRF. Age will be reported as collected in the eCRF for the CP543.5002 study. Baseline body mass index (BMI) will be calculated based on data from the preceding clinical trial, using the weight from the last visit and the height. Demographic characteristics will be summarized using descriptive statistics for all subjects in the Enrolled Population, and separately for all subjects in the Safety Population.

Sun Pharmaceutical Industries, Inc.
Statistical Analysis Plan – CP543.5002

Baseline characteristics will be summarized for both the “pre-zero” baseline and the CP543.5002 study baseline using descriptive statistics for the Safety Population by treatment group and overall and will include the following:

- baseline total SALT score
- baseline alopecia areata classification: scalp hair loss (SALT <50); partial scalp hair loss (SALT \geq 50 and < 95); complete or near-complete scalp hair loss (SALT \geq 95)
- whether the subject has experienced any past and/or concomitant diseases, conditions, exposures to serious infections, or past surgeries (as collected in CP543.3001 and CP543.3002)

The “pre-zero” baseline is defined as the last observation obtained prior to first dose of active drug in either CP543.5002 or the qualifying study. “CP543.5002 study baseline” is defined as the last observation prior to first dose in CP543.5002.

Other co-morbidities may be identified and included as baseline characteristics.

All demographics characteristics will be listed within a by-subject data listing for all enrolled subjects.

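### Does the post-dose-reduction analysis hide lost responses by counting SALT scores above 20 and up to 50 as no loss of response?

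*SAP*

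**What the plan says.** The opening of SAP 8.2.3.1 (Analysis of the Efficacy Endpoint Post-Dose Reduction) is redacted. What can be read is a set of definitions and one figure:

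- Loss: "Subjects with loss of response will be defined as having an absolute SALT score > 50". Its complement, SALT 50 or less, is no loss.
- Prior response: "Responders at pre-dose reduction baseline will be defined as having an absolute SALT score" of 20 or less at that baseline. Above 20 is a non-responder.
- A line graph of absolute change from the pre-dose-reduction baseline against visits since the reduction, for subjects reduced from "12 mg to 8 mg on or after 28 Apr 2023 due to the urgent safety measures".

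SAP 8.2.3 uses the same response level at every visit: "non-responders will be defined as having an absolute SALT score > 20". It plans a count of subjects at 20 or less by visit and treatment group, and a responder shift table from the pre-zero and CP543.5002 baselines. SAP 4.1 gives efficacy tables a separate column for subjects going from 12 mg to 8 mg BID, which "is defined similarly for qualifying dose changes from 12 mg BID to 8 mg BID". SAP 8.2.2 adds observed scores, absolute and relative change, and by-subject SALT listings, all without hypothesis tests.

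Protocol 4.2 calls SALT 20 or less "a measure that is considered to be clinically meaningful to patients and physicians". Protocol 8.4.1 uses it at Week 52 to decide who continues.

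**The concern.** Two thresholds are in use under related names. Response is gained at 20 or less, but it is recorded as lost only above 50. A subject in between fails the SAP's response definition and still falls under no loss. A reader shown a small loss percentage could conclude that response held after the reduction, when the figure says only that few subjects went above 50. SAP 8.2.3.1 is the section devoted to efficacy after a dose reduction made under an urgent safety measure, so its wording may be relied on in describing what happened to those subjects.

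**Working it through.** The plan states no figure to reproduce. The check applies its cut-offs and then asks which planned outputs show the middle group.

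**1. Labels.** Inputs: response is SALT 20 or less (SAP 8.2.3 and 8.2.3.1); loss is SALT above 50 (SAP 8.2.3.1). Relative change = 100 × (after − before) / before.

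| SALT before | SALT after | Change | Status after, 8.2.3 | Label, 8.2.3.1 |
|---|---|---|---|---|
| 10 | 20 | +10 (+100%) | responder | no loss |
| 20 | 21 | +1 (+5%) | non-responder | no loss |
| 20 | 35 | +15 (+75%) | non-responder | no loss |
| 10 | 50 | +40 (+400%) | non-responder | no loss |
| 20 | 60 | +40 (+200%) | non-responder | loss |
| 60 | 60 | 0 | non-responder | loss |

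Rows 2 to 4 are the concern. Row 2 also shows the case for a gap between the thresholds: with loss set at anything above 20, a one-point move would count. The last row would be odd if loss were tabulated for everyone. However, the section defines responders and non-responders at the pre-reduction baseline and no readable output there uses those groups, which suggests that the redacted text does.

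**2. What a loss percentage can tell.** Let N be the pre-reduction responders, L those above 50 and M those above 20 and up to 50. The share still at 20 or less is (N − L − M) / N. M can run from 0 to N − L, so this share lies between 0 and 1 − L/N. With assumed values N = 100 and L = 5, the range is 0% to 95%. The loss percentage only sets a ceiling on maintained response. The documents do not give M.

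**3. What else shows the group.**

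- *SALT 20 or less by visit, 12-to-8 mg column (SAP 8.2.3, 4.1).* This uses the right threshold but is indexed to study visit, not to the reduction.
- *Shift table (SAP 8.2.3).* Right threshold, but it starts from the earlier baselines.
- *Line graph (SAP 8.2.3.1).* Right baseline and time axis, but no categories. A general drift from 20 towards 50 would appear as a rise, though the readable text does not limit the graph to prior responders.
- *By-subject listings (SAP 8.2.2).* These allow M to be counted directly.

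**4. How far the by-visit table blurs.** The Protocol synopsis gives "Estimated date first patient enrolled: September 2021" and last completion in July 2024. Assume that the last subject completes Week 108 (Day 757), so enrolled 756 days earlier, between 6 June and 6 July 2022. On 28 April 2023:

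- first enrollees: 575 to 604 days on study; 575/7 = 82.1 and 604/7 = 86.3 weeks
- last enrollees: 296 to 326 days on study; 296/7 = 42.3 and 326/7 = 46.6 weeks

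If everyone were reduced on that date, visits strictly inside the widest span (42.3 to 86.3) are Weeks 44, 52, 60, 68, 76 and 84: 6 of 15 post-baseline visits could mix scores from before and after the reduction. The narrowest span (46.6 to 82.1) leaves 4. With reductions staggered over the next 8 weeks, the widest span reaches 86.3 + 8 = 94.3 and adds Week 92, making 7. None of these is a bound, because SAP 7.2 also allows changes from 12 mg to 8 mg at the investigator's discretion at other times. The count describes the 8.2.3 table and does not measure M.

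**The case for a change.** The strongest case for a change is that no readable output combines the response threshold of 20, the pre-reduction baseline and time since reduction. SAP 8.3 and 8.4 add no other efficacy endpoints or subgroups. A patient reduced shortly before Week 52 who goes from 20 to 30 would leave as a non-responder under Protocol 8.4.1 and yet carry the no-loss label. Such a patient might also miss the 12-to-8 mg column, since SAP 4.1 requires the changed dose to be dispensed at two or more consecutive visits and non-responders receive no drug at Week 52. Splitting prior responders into three levels would cost one more row and no new data.

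The description of the readable text stands, and the split would be a reasonable courtesy to readers. It does not show a defect, for three reasons.

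- The part of 8.2.3.1 that would specify the tabulation is redacted. No table of loss percentages is visible, so neither its absence of a middle category nor its population can be asserted.
- Setting loss further out than gain is a coherent choice. The SAP already places a severity boundary at 50 in its "baseline alopecia areata classification: scalp hair loss (SALT <50" for the mildest class. The support for 20 concerns reaching response at Week 24 (Protocol 4.2) and eligibility at Week 52 (Protocol 8.4.1); neither defines loss after a reduction.
- The definition is printed beside the label. A misreading requires the reader to ignore it.

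**Conclusion.** No change is called for. No loss of response, as readable in SAP 8.2.3.1, means SALT 50 or less. It includes prior responders who have risen above 20, so it should not be reported as response maintained at the SAP's own level. That is a caution for interpreting the results. The threshold is an explicit and fair choice, the possible gap lies in redacted text, and the middle group can be counted from the planned listings. If the study team wants the three-level split, SAP 8.1.2 already provides for exploratory analyses identified as such in the study report.

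The consequence is small: one supportive, descriptive analysis, with no hypothesis test, error rate or sample size attached. The number of subjects affected is unknown. The 0% to 95% range rests on invented counts and shows only what a loss percentage leaves open. The 4 to 7 mixed visits rest on estimated study dates and assumed timing of the reductions. This conclusion does not depend on the redacted text containing the split.
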